4.1.2 CONTROL

Usual CJOM will vary but details will be recorded including type of intervention and number and duration. Existing group probation-based perpetrator programmes will not be used as a comparator. Options to address offending behaviour will be grouped into the following categories:

- mental health treatment
- drug treatment •
- alcohol treatment
- education, training and employment
- relationships
- lifestyle and associates
- emotional management
- attitudes, thinking and behaviour
- compulsory unpaid work/ volunteering
- finance, benefits and debt

MONITORING COMPLIANCE: Men in both treatment arms will have a supervising PP/JSW to monitor compliance to the community sentences. Any violation of conditions will be referred back to court.

TRAINING: Facilitators, ISS workers and supervising PP/JSW will complete an online training course. Training and facilitator certification are delivered online and require a maximum of 30 hours of self-directed learning/assessment for Probation Officers (3 per PDU required) and 20 hours for integrated support service workers. The training includes the use of the SARA tool, a structured professional judgement tool specifically designed to assess risk and vulnerabilities in situations of IPV (the clinical/ risk lead is an accredited trainer). 63 Training includes modules on the ADVANCE-D intervention's theory of change; the importance of enhancing and maintaining motivation throughout; the content of the individual, group and website sessions and coaching phone calls, understanding the role of ISS, risk identification and reporting, case management and integrity support. The final two days will provide the opportunity for ADVANCE-D facilitators to practice delivery and be accredited to deliver.

4.2 DISCONTINUING ALLOCATED INTERVENTIONS

Any violation researchers become aware of will be referred to the PP/ JSW to consider referral to court. Alongside the RAR or CPO, men will have a supervising PP/ JSW to monitor compliance to the community sentences. Any violation of conditions will be referred back to court.

4.3 CONCOMITANT INTERVENTIONS PERMITTED OR PROHIBITED DURING THE TRIAL

Men can receive treatment and support for their substance use. They should not be receiving (structured) interventions for IPV perpetration. Men in the control arm will NOT receive ADVANCE-D at the end of the 20 weeks of delivery to the treatment arm.

5. ASSIGNMENT OF INTERVENTIONS

5.1 RANDOMISATION METHOD

To reduce selection and recruitment bias, PDU/JSWTs will be randomly allocated to experimental or control arms in a 1:1 ratio to deliver ADVANCE-D+CJOM or usual CJOM. The sequence will be generated by the King's Clinical Trials Unit (KCTU)-affiliated statistician, using block covariate minimisation at the cluster level developed by Carter and Hood.⁶⁶ The following covariates will be used for the clusters: % non-white ethnicity, size of unit/team, index of multiple deprivation (IMD) by decile^a and classification of region (urban/rural)^b. Cluster allocation will then be communicated to the trial manager, who will then inform the PDU/JSWT. PDU/ JSWT make decisions on the CJOM required to address any treatment/support recommended by court.

^aIMD data obtained from:

England: https://imd-by-postcode.opendatacommunities.org/imd/2019

Scotland: https://www.gov.scot/publications/scottish-index-of-multiple-deprivation-2020v2-postcode-look-up/

^bClassification of region data obtained from:

England: https://www.nomisweb.co.uk/sources/census 2021 pc

Scotland: https://www.gov.scot/publications/scottish-government-urban-rural-classification-2020/pages/1/

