3. PARTICIPANTS

3.1 STUDY SETTING & RECRUITMENT

Courts mandate sentences to men convicted of IPV. Sentences include a rehabilitation activity requirement (RAR) in England; or a community payback order (CPO) in Scotland. These requirements/orders are given with a view to promoting the offender's rehabilitation and reduce the likelihood of reoffending. Men must see a Probation Practitioner (PP) at a Probation Delivery Unit (PDU; England)/ Justice Social Worker (JSW) at a Justice Social Work team (JSWT; Scotland) within 5 days post sentencing when sentence planning will take place. PDU/ JSW team make decisions on the offender management required to address any support recommended by court. Alongside the RAR or CPO, men will have a supervising PP/ JSW to monitor compliance to the community sentences. Any violation of conditions will be referred back to court.

There are 11 probation regions in England. PDU are the local units in each of these probation regions. For example, Greater Manchester (probation region) has 9 local PDU (see Table 1). Scotland has 32 Justice Social Work areas (JSW area) that provide statutory criminal justice services in JSWT. For example, City of Edinburgh (JSW area) has 2 local JSW teams (see Table 1). PDU and JSWT will be treated as clusters for the purpose of the trial.

To be eligible to take part in the trial, PDU and JSWT must have a central intervention delivery model (e.g. a central intervention delivery team in Greater Manchester deliver interventions across all 9 PDU); have trained and certified facilitators and partner support workers; and not be sites in other intervention trials. Facilitators in each Probation Region (England) and JSW area (Scotland) will be trained to centrally deliver the ADVANCE-D Programme and will be blind to allocation of PDU/ JSWT. Each PDU/ JSWT will recruit and consent 14 men to the trial before the outcome of allocation is known to them.

A total of 32 PDU/ JSWT are required for the cRCT. Twelve PDU/ JSWT (clusters) from the 24 clusters in Table 1 will be allocated at random for men to receive the ADVANCE-D Programme delivered by a central team + usual community justice offender management (CJOM) (Option 1) OR usual CJOM (Option 2) during the internal pilot from two probation regions from England (Greater Manchester and the North West) and one JSWT from Scotland (City of Edinburgh). An additional 20 PDU/ JSWT will be recruited to the main trial.

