10.4 STATISTICAL METHODS FOR PRIMARY AND SECONDARY OUTCOMES

10.4.1 STATISTICAL METHODS FOR PRIMARY OUTCOME

We will analyse the primary outcome using multi-level linear regression model, including assessments at 4 and 12 months to assess the difference in ADVANCE-D and control at 12-months (primary assessment time-point). Participants and PDU/JSWT will be fit as random effects, and pre-specified fixed effects for participant age, baseline IPV severity, and baseline ABI total score, and region. The adjusted mean difference (aMD) in the Abusive Behavior Inventory (ABI) total score between those from ADVANCE-D with CJOM compared to Usual CJOM will be presented with the associated two-sided confidence intervals (95% CI) and p-value, and intraclass correlation coefficient (ICC). The analysis will use the ITT population that will include all participants who were followed up at either the 4- or 12-month time-point. Pattern missingness will explore the missing data. A CACE will be developed as a sensitivity analysis to the primary analysis. Sensitivity analyses will be used for modelling the different intercurrent events. An additional sensitivity analysis will use the partner IPV data.

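### Clusters are not balanced on probation region, JSW area or country, although the primary model adjusts for region and the programme is delivered by region; the power cost is small with 2–3 regions and grows with more

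*Protocol*

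**What the plan says.** **Allocation (Protocol 5.1).** Clusters are allocated 1:1 "using block covariate minimisation at the cluster level". The factors begin "The following covariates will be used for the clusters: % non-white ethnicity, size of unit/team, index of multiple deprivation (IMD") by decile and end with "classification of region (urban/rural"). Footnotes take deprivation and urban/rural class from separate English and Scottish sources. Sections 5.1 to 5.3 state no stratification by probation region, JSW area or country.

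**Primary model (Protocol 10.4.1).** Participant and PDU/JSWT are random effects, with "pre-specified fixed effects for participant age, baseline IPV severity, and baseline ABI total score, and region". The section does not say what region means.

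**Setting (Protocol 3.1).** The word is used here for the English probation regions, of which there are 11. Facilitators are trained in each probation region or JSW area and deliver centrally to its clusters. Greater Manchester has 9 PDUs, and "City of Edinburgh (JSW area) has 2 local JSW teams".

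**The concern.** With region as a fixed effect, the treatment effect is estimated from contrasts within regions. A region split unevenly between arms contributes less than its share, and one lying wholly in one arm contributes nothing. Balancing on the factor avoids that loss. The protocol adjusts for region but leaves its balance to chance.

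The document itself shows that geography matters. Delivery teams belong to a region or JSW area. The sentence differs by country (rehabilitation activity requirement or community payback order), and so do the screening instruments (OASys and the substance use screen in England, LS/CMI and SARA V3 in Scotland). The deprivation and urban/rural factors cannot stand in for country, because clusters from either country can share a decile or a class.

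At stake are some power and the even spread of intervention clusters over delivery teams. The allocation factors also cannot be repaired later: an analysis plan can define region, but it cannot rebalance clusters already allocated.

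**Working it through.** **The plan's own figures (10.3).** An effect size of 0.4 with 90% power and two-sided 5% gives 264 by the normal formula and 266 by the t-test, which matches the stated 266. The design effect with 13.5 men per cluster and ICC 0.03 is 1 + 12.5 × 0.03 = 1.375, and 266 × 1.375 = 366, against a stated 358 (2.2% apart). Normal-approximation power for 26 × 13.5 men is 89.2%. The sample size is reproduced closely enough to build on.

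**Starting power as randomised.** Inputs from 10.3 are 32 clusters, 14 men each, 18% dropout, ICC 0.03 and effect 0.4.
- Men analysed per cluster: 14 × 0.82 = 11.48; in total 32 × 11.48 = 367.4.
- Design effect: 1 + 10.48 × 0.03 = 1.314; effective sample 367.4 / 1.314 = 279.5.
- z = 0.4 × √(279.5/4) = 3.344; power = Φ(3.344 − 1.960) = 91.7%.

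**Information kept under region-blind allocation.** With region fixed effects, information on a cluster-level treatment is proportional to the sum over regions of n_T × n_C / n. Perfect balance gives 32/4 = 8. For a random 16:16 allocation that ignores region, a region of n clusters has E[n_T × n_C] = n(n − 1) × 256/992. Summing over R regions gives (256/992)(32 − R), and dividing by 8 gives a kept fraction of (32 − R)/31. Power is then Φ(3.344 × √kept − 1.960).

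| Regions R (assumed) | Kept | Power |
|---|---|---|
| 2 | 30/31 = 97% | 90.8% |
| 3 | 29/31 = 94% | 89.9% |
| 4 | 28/31 = 90% | 88.8% |
| 6 | 26/31 = 84% | 86.5% |
| 8 | 24/31 = 77% | 83.7% |

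**Simulation check.** I drew 20,000 region-blind 16:16 allocations per layout (11.5 men per cluster) and compared the average power with the best balance achievable within regions, using the same model. The layouts are invented.

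| Assumed layout | Region-blind | Balanced | Worst 5% of allocations: at or below |
|---|---|---|---|
| 9/21/2 | 89.8% | 91.6% | 86.5% |
| 9/9/9/5 | 88.6% | 91.3% | 82.0% |
| 9/8/6/5/2/2 | 86.1% | 91.5% | 78.6% |
| eight of 4 | 83.0% | 91.7% | 70.9% |

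These use the normal approximation. A t reference lowers both power columns by about 2 to 3 points and leaves the gap similar.

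**Where one-sided splits occur.** For a region of 9 clusters among 32, the probability that all fall in one arm is 2 × C(16,9)/C(32,9) = 0.08%, and a split of 7:2 or worse has probability 11%. For an area with two participating teams, both fall in the same arm with probability 15/31 = 48%. The risk therefore sits with small areas.

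**The case against.** **The word is undefined.** The only region item in 5.1 is the urban/rural class, which is balanced. If 10.4.1 means that class, there is no power loss of this kind. This stands as a real alternative reading. Section 3.1 favours the geographical reading without settling it. Under the urban/rural reading, country and delivery region are left both unbalanced and unadjusted, so the text needs attention either way.

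**The number of regions is not stated.** With two levels (country, for example) power stays above 90%, and with three it is 89.9%. This stands, so the size has to be given as a range.

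**Region may pay for itself.** If it explains between-cluster variance, the loss is smaller. With a residual ICC of 0.02 (assumption) the design effect is 1 + 10.48 × 0.02 = 1.210, and power at R = 4 is 91.2%. Balanced allocation would then give 93.6%, so part of the loss remains avoidable. Adjusting for baseline ABI also helps. If it explains 16–25% of the variance (assumption), power is about 93–96% at R = 4 and 89–93% at R = 8, against 95–97% with balance.

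**Block minimisation is not simple random allocation.** Ethnicity, deprivation or the blocks may bring some incidental balance by region. That is possible, but nothing secures it.

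**Stronger readings the documents do not support.**
- A reader might infer that whole regions are likely to land in one arm. For the one region whose size is given, this is very unlikely.
- A reader might cite the two Edinburgh teams as a pair at risk within the 12-cluster pilot. Section 3.1 also speaks of one JSWT from Scotland in the pilot, so that pair cannot be assumed.
- A reader might say that usual offender management is regional. The protocol describes only programme delivery that way; the PDU/JSWT decides offender management.

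**Conclusion.** The point holds as an avoidable inefficiency of modest and uncertain size. Section 5.1 leaves out the geographical factor that 3.1 makes the unit of delivery and that 10.4.1, on its more natural reading, adjusts for.

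Under the geographical reading the average cost is about 1 to 2 points of power with 2 or 3 regions, 3 with 4, 5 with 6 and 8 with 8. Average power drops just below the 90% target at 3 regions and clearly below it from 4. These figures assume the number of regions, an ICC that stays at 0.03 after region is fitted, the normal approximation and allocation independent of region.

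A reader might infer that the primary test is biased or invalid, or that adjusting for region throws power away for no return. Neither follows: adjusting for an unbalanced factor is legitimate, and region may remove real between-cluster variance. The case is for balancing on it as well.

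**What to change.** In 5.1, add geographical region (probation region or JSW area, with small JSW areas pooled, and at the very least country) as a factor in the block minimisation for every cluster not yet allocated. In 10.4.1, state that region is this same factor, with the same grouping. Pooling matters for the model too: an area entered as a single cluster with its own fixed effect contributes nothing to the treatment contrast.

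The programming cost is one more factor. The statistical cost is slightly looser balance on the four existing factors. There is also some predictability in very small areas: with two teams forced apart, the first allocation reveals the second, while the protocol relies on practitioners being blind at consent. Pooling small areas and allocating clusters in blocks limits this. Clusters already allocated need no change; later blocks can take their positions into account.

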5.2 CONCEALMENT MECHANISM

Randomisation sequence is generated, and the clusters are assigned treatment groups after baseline data is collected. These allocations will be communicated to the trial manager. The sequence will be generated following a randomisation protocol that will ensure that the senior statistician remains blinded throughout the duration of the study. Facilitators who are not responsible for supervising men in probation will be trained to centrally deliver ADVANCE-D and therefore will be blind to which PDU/ JSWT men are attending. Supervising officers in probation or JSWT will be blind when they consent men to the trial. Researchers will be blind when they conduct baseline interviews with men in the trial.

5.3 RANDOMISATION IMPLEMENTATION

5.3.1 ALLOCATION SEQUENCE GENERATION

A KCTU statistician will generate the randomisation sequence. This allocation list will be communicated to the trial manager who holds the randomisation key assigning A or B to intervention in order to implement the assigned allocations within the clusters. This process will continue per PDU/JSWT until all clusters have been allocated. Once the sequence is generated, a PDF of the allocations will be stored as source data. The Chief Investigator, Senior Statistician and TMG will be blinded to the sequence generation.

5.3.2 ENROLMENT OF PARTICIPANTS

Participants will be enrolled in the study for the purpose of $CONSORT^{84}$ reporting at the point of signing a consent form and will be part of the target N=450 at the point of randomisation.

5.3.3 ASSIGNMENT OF PARTICIPANTS TO INTERVENTIONS

PDU/ JSWT will be assigned by a KCTU statistician and they will inform the trial manager of allocation. We will close recruitment once we have an adequate number of men consented and baselined at each PDU/ JSWT within a period of two weeks. At this point, the trial manager will advise the PDU/ JSWT of allocation.

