A researcher will then text or call the consented participant and complete the baseline interview with the participant in person at the PDU/JSWT or by phone or video call. All men from a cluster should be baselined within two weeks. This call will not be undertaken in the presence of a PP/ JSW. During this call, researchers will check the participant still wishes to take part in the trial, that they have consented to take part in the trial of their own free will and are fully informed of what taking part in the study involves. Participants will have the opportunity to opt out of the trial at this point without any repercussions to their CJOM. This timeframe allows the participant up to two weeks from consenting to take part to decide whether they still wish to take part.

A researcher will be responsible for completing a baseline interview with consented men by phone, video conferencing, or in person at the PDU/JSWT. This will not be conducted in the presence of a PP/JSWT. Interviews will never be conducted in participants' homes.

Only after the men are consented and baselined in each PDU /JSWT and their female current or expartners have been consented and baselined; will participants and PDU/ JSWT team be told what treatment arm they have been allocated to.

For current or ex-partners

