The PP/ JSW will securely pass the contact details of victims/ survivors to the trial manager using a password protected document via encrypted e-mail, a secure Microsoft Teams channel or via another secure method (e.g. Criminal Justice Secure Email). This is standard practice in community perpetrator interventions to ensure safeguarding and risk are managed and is included in the Home Office Standards for Domestic Abuse Perpetrator Interventions.⁶⁴ The Information Commissioner's Office have stated that a service can potentially use legitimate interest as a lawful basis to gather this information suggesting the individual (ex)-partner would reasonably expect you to use their data in this way (Case Reference Number ENQ0782120). Researchers need current or ex-female partners' details to invite them to take part in the research by providing outcome data, and to share their details with the women's support service who will contact them to offer support, assess risk and signpost for additional needs. Clear and regular lines of communication between probation/justice social work, women's support services and the research team are necessary so that any changes in risk can be identified and appropriate actions taken to ensure that current and ex-female partners are effectively safeguarded. While all current and/or ex-partners of men in the ADVANCE-D intervention will be offered support, only the current or ex-partner connected to the index IPV event will be recruited to the study. Following male participants' baseline assessment, researchers will text or email their (ex)-partners with brief information about the study and advise that they will be phoning them. A

script and short explanation video about taking part in the study has been developed with the women's people with lived experience panel to facilitate this.

To maximise safety and convenience, there will be the option to select a time slot for the call. Within a week, a researcher will contact the (ex)-partners to:

- 1. Inform them their (ex)-partner is participating in the study.
- 2. Read the PIS and explain what taking part involves.
- 3. Invite them to participate in the research (baseline and follow up interviews, qualitative interviews and data linkage at 24 months).
- 4. Explain limitations to confidentiality.
- 5. Advise them that an integrated support service (ISS) worker will call to offer them support only if their current or ex-partner is allocated to receive the ADVANCE-D Programme.

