Women interested in taking part in the research will be emailed, sent a message on WhatsApp or mailed a copy of the PIS and consent form by the researcher. Before the baseline assessment takes place, the researcher will check with participants whether they have somewhere quiet and private to talk and ensure that they are safe to talk. Researchers will be responsible for recruitment, consent and baseline interviews with (ex)-partners. (Ex)-partners will be given the option for questionnaires to be administered by the researcher in person, by phone or video call. Face-to-face recruitment or interviews will take place in probation, women's support services or other services such as children's centres or libraries. The researcher that completes the questionnaires with the partner will be a different researcher to the one that completed the baseline assessment with the male participant to avoid inadvertent disclosure of information.⁹⁷ All research participants have the right to refuse to answer questions if they do not wish. Interviews will never be conducted in (ex)-partners' homes.

Only after recruitment and the baseline interview with (ex)-partners has been completed or the (ex)partner has declined the offer to participate in the trial or the (ex)-partner is not contactable, will the allocation of PDU/ JSWT be known to researchers and PDU/ JSWT.

Women whose current or ex-partners are in a PDU/ JSWT allocated to receive the ADVANCE-D Programme, will be contacted by an ISS worker to offer support regardless of whether the woman wishes to take part in the research. If researchers have been unable to contact the female (ex)-partners, they will pass the contact details to the ISS workers who will attempt to call them to offer support. Women whose current or ex-partners are in the control arm of the study will receive whatever the usual support to partners would be, if any.

For staff

Staff at each service involved in delivering the intervention (PDU or JSWT) or supporting women whose partners are receiving the intervention (ISS) will be invited to take part in focus groups or interviews throughout the duration of the study about their experiences. This process is explained to services as part of their contract when they agree to be involved in the study.

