5.4 BLINDING STATUS OF RESEARCHERS

Researchers (outcome assessors) will be blind to group allocation when baseline interviews with male participants and their current or ex female partners are conducted. After the men are baselined from each PDU/ JSWT and their (ex)-partners have been completed their baseline assessment or declined to take part in the research or were not contactable, they will be informed of allocation. Probation practitioners and principal investigators/other staff at PDU/ JSWT will be blind during eligibility and consent.

Individual blinding status	Blinded	Unblinded
Chief Investigators	X	
Principal Investigators and all other PDU/JSWT staff at site (blinded until post baseline)		X
Co-applicants ^α	X	
Trial Manager		X
Facilitators		X
Senior Trial Statistician	X	
Trial Statistician ^a	X	
Senior Health Economist	X	
Health Economist (blinded until after data collection)	X	
Trial Participants		X
Outcome Assessors (blinded during baseline interview)		X
Partner Support Workers		X
Trial Steering Committee (TSC)	X	
Data Monitoring Committee (DMC)		X

Table 6. Blinding Status

^aThe blinding status of the research team is detailed in Table 6 above. Note the Trial Statistician will become partially blinded at the point of reporting to the Data Monitoring Committee outcome and safety data partitioned in groups labelled A and B. The time of when this planned change in blinding status of the Trial Statistician is will be reported. The Clinical Lead (co-applicant [name]) will be unblinded.

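### Section 5.3.3 lets a site be told its arm once the men are baselined, whereas Section 3.3 withholds it until the women have been dealt with as well

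*Protocol*

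**What the plan says.** Section 5.3.3 gives the trial manager a trigger and an action. The trigger is "We will close recruitment once we have an adequate number of men consented and baselined at each PDU/ JSWT", within a period of two weeks. The action follows directly: "At this point, the trial manager will advise the PDU/ JSWT of allocation". Women are not mentioned.

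Section 3.3 sets a later point, twice. In the part on men, participants and the PDU/JSWT team learn the arm "Only after the men are consented and baselined in each PDU /JSWT and their female current or expartners have been consented and baselined". In the part on partners, the condition is "Only after recruitment and the baseline interview with (ex)-partners has been completed", or that she has declined or cannot be contacted; only then "will the allocation of PDU/ JSWT be known to researchers and PDU/ JSWT".

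Section 5.4 sets the parallel rule for researchers. They "will be blind to group allocation when baseline interviews with male participants and their current or ex female partners are conducted", and they are informed "After the men are baselined from each PDU/ JSWT and their (ex)-partners have been completed their baseline assessment or declined to take part" or could not be contacted.

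Section 3.3 also fixes the order of approach. A researcher texts or emails the woman after the man's own baseline and phones within a week. Among the things the researcher must do on that call is "Advise them that an integrated support service (ISS) worker will call to offer them support only if their current or ex-partner is allocated" to ADVANCE-D.

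**The concern.** The women's offer depends on the arm. In intervention clusters a support worker contacts every partner, whether or not she joins the research, and is given the details of women whom the researchers could not reach. In control clusters women receive whatever support is usual, if any. A woman who learns the arm before she consents, or before she answers the baseline questions, therefore knows whether that offer applies to her.

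If the site is told under 5.3.3 while some partners are outstanding, the arm can reach those women through site staff, through the men, or through support workers who call in one arm only. Two things could then differ by arm: which women agree to take part, and what they report at baseline.

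The data at stake are the partner-reported secondary outcomes (ABI-R, CBS-R, feeling of safety and the rest) and the sensitivity analysis on partner IPV data in Section 10.4.1. Section 10.4.2.1 has continuous secondary outcomes analysed like the primary, which adjusts for the baseline score. If the women's models do the same, a baseline taken after disclosure would enter as a covariate. Disclosure to a cluster cannot be undone.

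**Working it through.** The protocol gives no figure on this point, so the check is a comparison of the rules, followed by their timing.

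**The rules side by side**

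| Place | Condition on men | Condition on women | Who then learns the arm |
|---|---|---|---|
| 5.3.3 | adequate number consented and baselined | none | PDU/JSWT |
| 3.3, men | consented and baselined | consented and baselined, no exceptions | participants and PDU/JSWT team |
| 3.3, partners | not restated | baselined, declined or not contactable | researchers and PDU/JSWT |
| 5.4 | baselined | baselined, declined or not contactable | researchers |

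Rows 1 to 3 all name the PDU/JSWT, so they cannot be reconciled as rules for different audiences. The other relevant places do not settle it. Section 5.2 assigns clusters after baseline data, Section 5.5 unblinds site staff after baseline measures, and Table 6 has site staff blinded until after baseline; none says whose baseline. The sentence in 5.2 on blind baseline interviews names men only.

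**Whether the rules give different dates**

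Inputs: the men's baselines fall within two weeks of all men in the cluster being consented (Section 3.4.5). The woman is texted after the man's baseline and phoned within a week (Section 3.3). Assumption: the week runs from the day of the man's baseline.

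- Count days from the point at which all men in the cluster have consented. A man baselined on day d has a partner who is phoned by day d + 7 at the latest.
- If the last man is baselined on day 14, 5.3.3 permits release on day 14.
- The partner's call can fall after release when d + 7 > 14, that is, when d > 7.
- For the last man the call may come as late as day 14 + 7 = 21, and consent and baseline come after the call.

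The partners at risk are therefore those of men baselined in the second week. Partners of men baselined in the first week should already have been phoned, though not necessarily interviewed. Seven days is a maximum, so actual overlap may be smaller.

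**Size of the partner data set**

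Section 3.7.1 reports that two earlier studies recruited 26% and 47% of partners, with 63% and 52% of those followed up at 4 months. If those rates applied to 450 men:

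- recruited: 450 × 0.26 = 117, and 450 × 0.47 = 211.5, about 212
- followed up at 4 months: 117 × 0.63 = 73.7, about 74, and 211.5 × 0.52 = 110.0

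These are the sizes of the whole partner sample. They measure neither the share recruited after disclosure nor any bias.

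**The case against.** The best case for the protocol is that the protective rule is stated more than once. Section 3.3 gives it twice in restrictive terms, and Section 5.4 repeats it for researchers. Table 4 places the woman's baseline in week 2 and the support worker's first contact in week 3. Section 5.3.3 is silent about women; it does not say to release regardless of them, and a careful trial manager could read it together with 3.3. This stands as evidence of intent, and it marks 5.3.3 as the outlier. It does not remove the conflict, because 5.3.3 names the person, the trigger and the moment, and that moment can come before the one in 3.3.

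A reader might go further and infer three things that the documents do not support.

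- *That researchers would recruit and interview women unblinded.* Section 5.3.3 informs the PDU/JSWT only. Researchers handle the women's recruitment, consent and baseline, and stay blind under 3.3 and 5.4. What remains is indirect leakage through site staff, men or support workers.
- *That most women would still be unapproached at release.* Approach is rolling, following each man's own baseline, so only partners of the later men are clearly exposed.
- *That the two earlier recruitment rates show the possible imbalance.* Assigning 47% to one arm of 225 men and 26% to the other gives 225 × 0.47 = 106 against 225 × 0.26 = 59. But the rates come from two different studies, say nothing about disclosure, and count women recruited, not analysed. Equal uptake would not rule out bias either, since equal rates can hide different kinds of women.

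**Conclusion.** The contradiction is real and nothing in the protocol resolves it. Followed as written, 5.3.3 can disclose the arm to a site before the partners of later-baselined men have consented or been baselined, contrary to 3.3.

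The consequence is bounded. It arises only if 5.3.3 is applied without 3.3, and it falls on the women's secondary outcomes and the partner-data sensitivity analysis. The primary outcome is the men's own report, and the release rules in 3.3, 5.3.3 and 5.4 all place the men's baseline before disclosure. The sample size is unaffected. The direction and size of any bias cannot be estimated: that would need the number of women recruited after release and the effect of knowing the arm on uptake and answers, and the protocol gives neither. The case for changing the text rests on the clarity of the conflict and the small cost of removing it.

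**What to change.** - **Section 5.3.3:** state the release point used in the partner part of 3.3 and in 5.4. The trial manager informs the PDU/JSWT only when every man in the cluster is baselined and every index partner is logged as baselined, declined or not contactable.
- **Section 5.2:** extend the sentence on blind baseline interviews to the partners' interviews.
- **Section 3.3, men's part:** add the declined and not-contactable exceptions. As worded, one woman who declines would block release indefinitely.
- **Optional:** set a cut-off after which an unreached partner is logged as not contactable, so that one outstanding call does not hold up a cluster.

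The cost is a few sentences and a release log. Some clusters will be told their arm slightly later than 5.3.3 alone would allow, a delay that Section 3.3 already implies.
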